### 6.3 OTHER ENDPOINTS

#### Primary endpoint

Patients with cardiac fixation at the radionuclide bone scintigraphy and/or SPECT performed with 99mTc-DPD or 99mTc-PYP or 99mTc-HMDP will be defined as patients with a cardiac retention of grade 1, grade 2 or grade 3.

Patients without cardiac fixation at the radionuclide bone scintigraphy performed and/or SPECT with 99mTc-DPD or 99mTc-PYP or 99mTc-HMDP will be defined as patients with a cardiac retention of grade 0.

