### **6.4 COVARIATES**

- Grade (0, 1, 2, 3) and for grade 2&3 pooled together
- Age in class 50 – ≤60 ; >60 – ≤70 years ; >70 – ≤80 years ; > 80 years]
- Gender (Male/Female)
- Cardiological symptomatology (Yes/No, where patient with a cardiological symptomatology are defined as patient with a least one cardiological manifestation (point 7 in 0)
- High Creatinine, high BNP and high NTproBNP (See Section 6.3, § 8)

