## **8 STATISTICAL METHODOLOGY AND STATISTICAL ANALYSES**

### **8.1 STATISTICAL METHODS**

Quantitative variables will be described using number of filled and missing data, mean, standard deviation, median, 1st and 3rd quartiles, minimum and maximum. The 95%CI of the mean will also be provided, assuming a normal distribution. In case of departure from normality, results will be interpreted based on median and Interquartile Range (IQR).

Qualitative variables will be described using number of filled and missing data and, for each modality, the frequency and percentage (referring to filled data). A 95% confidence interval (CI) will be associated to binomial proportions using the Wilson score method.

Factors associated to an outcome of interest (ATTR vs other and ATTRwt vs ATTRv within patients diagnosed with ATTR-CM) will be identified using univariate logistic regression models. A separate logistic regression model will be created for each factor (as well as covariates described in section 6.4). If the variable is significantly associated to the outcome at the 10% level then the factor will be put forward into a multivariate model. Once the univariate model selection is complete, backwards selection will be used to remove factors from the multivariate model which do not have a significant p value at the 5% level. The covariate with the highest p value will be removed in turn until all factors have a p value less than 0.05. If a significant interaction is found then the individual factors of this interaction will be kept in the model, regardless of their p value. A significant interaction is tested for between all variables in the multivariate model.

Furthermore, a table showing all of the 95% confidence intervals and p values for the odds ratios coming from the univariate and multivariate models will be created.

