### 5. Factors associated to positive scintigraphy

Factors associated to positive scintigraphy will be identified in the FAS1 by univariate and multivariate logistic regression. This analysis will be performed in the FAS1 population and will include all variables collected in the CRF for both positive and negative scintigraphy. Clinical laboratories will be excluded from this analysis as only available for positive scintigraphy.

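### Scintigraphy grade is left as a candidate covariate in logistic models whose outcome is defined by grade, so its odds ratio cannot be estimated and, depending on an unnamed test, it can displace the other factors

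*SAP*

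**What the plan says.** SAP 6.4 (Covariates) begins its list with "Grade (0, 1, 2, 3) and for grade 2&3 pooled together" and ends it with "High Creatinine, high BNP and high NTproBNP". SAP 8.1 makes all of these candidates: "A separate logistic regression model will be created for each factor (as well as covariates described in section 6.4". Selection then has two steps. At entry: "If the variable is significantly associated to the outcome at the 10% level then the factor will be put forward into a multivariate model". At removal: "The covariate with the highest p value will be removed in turn until all factors have a p value less than 0.05". Section 8.1 also asks for a table of odds-ratio confidence intervals and p-values from all the univariate and multivariate models. It does not say whether p-values come from Wald, likelihood-ratio (LR) or score tests.

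The outcomes are these:

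- **Positive scintigraphy** (SAP 8.2, Other analyses, item 5): "Factors associated to positive scintigraphy will be identified in the FAS1 by univariate and multivariate logistic regression". SAP 6.3 says that patients with fixation "will be defined as patients with a cardiac retention of grade 1, grade 2 or grade 3"; grade 0 is negative.
- **Grade 2-3 vs negative patients**, in FAS1 (item 6).
- **ATTR**, defined in SAP 6.3 as grade 2-3 without monoclonal protein abnormality. Section 8.1 calls the contrast ATTR vs other without naming a set; item 6 places the ATTR-CM model in FAS2 and FAS3.
- **ATTRwt vs ATTRv** among ATTR patients (8.1), defined by genotype.

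For the two FAS1 models the candidates are all CRF variables recorded in both positive and negative patients. Grade is one of them. The only exclusion is: "Clinical laboratories will be excluded from this analysis as only available for positive scintigraphy".

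**The concern.** A variable that defines the outcome cannot be a candidate factor for it. Grade fixes the first two outcomes exactly and is a necessary condition for ATTR. Followed as written, the plan fits models with no finite maximum-likelihood estimate for grade and tabulates whatever the software returns when it stops. Whether grade then reaches the multivariate model, and displaces age, sex or carpal tunnel syndrome, depends on a choice of test that the SAP leaves open. Identifying factors associated with ATTR amyloidosis is a named analysis in Protocol 9.7, so these tables will be read.

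Monoclonal protein results raise the same difficulty in the ATTR models, because their absence is the other half of the ATTR definition. The reason given for excluding laboratory variables in items 5 and 6 does not apply within FAS2 or FAS3, where those results can be available.

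**Working it through.** **1. The plan's own figures.** The documents give no sample size or power for the logistic models. The only design figures are in Protocol 9.5, and both reproduce: 1.96 × √(0.10 × 0.90 / 1500) = 1.52%, stated as ±1.5%; 1.96 × √(0.30 × 0.70 / 150) = 7.33%, stated as ±7.3%. They do not bear on this point.

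**2. Event rate within each grade, from the SAP definitions alone.**

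| Outcome | Grade 0 | Grade 1 | Grade 2 | Grade 3 | Separation |
|---|---|---|---|---|---|
| Positive vs negative | 0% | 100% | 100% | 100% | complete |
| Grade 2-3 vs negative | 0% | not included | 100% | 100% | complete |
| ATTR vs other, FAS1 | 0% | 0% | mixed | mixed | quasi-complete |
| ATTR vs other, FAS2 | – | 0% | mixed | mixed | quasi-complete |
| ATTR vs other, FAS3 | – | – | mixed | mixed | none |
| ATTRwt vs ATTRv | – | – | mixed | mixed | none |

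With grade as a factor, the fitted log-odds in a grade is ln(events / non-events). It is infinite wherever the rate is 0% or 100%. This holds for any data set.

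**3. What the selection rule does.** Simulated cohorts, with assumptions that are not in the documents: grades 1/2/3 split 20/30/50% among positives; 20% with monoclonal abnormality; true log odds ratios of 0.08 per year of age, 0.8 for male sex and 1.2 for carpal tunnel syndrome (CTS). Scenarios: N = 1500 with 10% or 20% positive, and N = 1000 with 10%. In the first, the counts in grades 0/1/2/3 were 1348/28/44/80, that is 152 positive.

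*Positive vs negative.* Null −2 log L = −2[152 ln(152/1500) + 1348 ln(1348/1500)] = 984.0. With grade in the model it falls to about 0.
- LR and score tests: across scenarios and both completely separated outcomes, p for grade is below 1e-120, so grade passes the 10% screen.
- Wald test: standard errors run from about 5,000 to 10,000 and p is about 1, so grade fails the screen.
- The Wald value depends on where the fit stops. In a separate simulation (N = 1500, 10% positive) p was 0.15-0.27 after 8 iterations and about 0.98 after 25. All of these exceed 0.10.

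*Effect on the other factors once grade is in the model* (N = 1500, 10% positive; LR p for age, male sex, CTS):

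| Outcome | Without grade | With grade |
|---|---|---|
| Positive vs negative | 7e-21, 2e-4, 3e-10 | 1, 1, 1 |
| Grade 2-3 vs grade 0 | 8e-17, 1e-3, 9e-7 | 1, 1, 1 |
| ATTR vs other, FAS1 | 2e-12, 0.04, 9e-4 | 0.95, 0.14, 0.27 |
| ATTR vs other, FAS2 | 0.63, 0.17, 0.024 | 0.95, 0.14, 0.27 |
| ATTR vs other, FAS3 | 0.98, 0.16, 0.22 | 0.95, 0.14, 0.27 |

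The last three rows agree in the right-hand column because, once grade is in, patients in grades 0 and 1 add nothing to the likelihood. All three fits then rest on the same 44 + 80 = 124 grade 2-3 patients. In FAS2 there was little signal to lose; the marked loss is in FAS1.

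*ATTR vs other, grade itself, in FAS1 or FAS2:* LR p from 1e-10 to 1e-175, Wald p from 0.5 to 1, standard errors from about 1,700 to 16,000. Within FAS3 and for ATTRwt vs ATTRv, standard errors were 0.3 to 0.7 and the fits were ordinary.

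**4. Monoclonal results.** Within FAS3, ATTR is by definition the absence of monoclonal protein abnormality. That status therefore separates ATTR from other completely, even though grade does not.

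**The case against.** - **Grade may be meant only for display.** SAP 5.1 plans analyses of grade 1 against grades 2 and 3, 8.2 item 3 describes variables by grade, and the table shells have grade columns. This is a plausible intention, but 8.1 refers to the 6.4 list by number and nothing withdraws grade. SAP 3 says the publication interim left out the multivariate analyses, so the documents show no earlier run of that step.
- **Multivariate entry is conditional.** A reader might infer that every 6.4 covariate goes into the multivariate model, or that grade always eliminates the other factors. The text does not support that. Only the univariate fit is mandatory; entry needs p < 0.10, and the Wald p-values above would screen grade out. Displacement needs an LR or score test.
- **Separation is not general.** A reader might take complete separation to apply to both outcomes named in 8.1. It does not: ATTR vs other is at most quasi-complete, and ATTRwt vs ATTRv is not separated.
- **Laboratory variables are already excluded from the two FAS1 models**, and Protocol 9.3 classes IFE and sFLC as clinical laboratories. This stands: a specific exclusion limits the general list in 6.4. What remains is to align 6.4 with it and to deal with IFE/FLC in the ATTR models.
- **The tests are exploratory** (SAP 4.2). This also stands, and it limits the weight of the point.

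**Conclusion.** The point holds as a defect in a stated rule, confined to certain models. Separation is complete for positive scintigraphy and for grade 2-3 vs negative, and quasi-complete for ATTR vs other in any set that includes grade 0 or 1. It follows from the SAP's definitions and needs no assumption about prevalence or effects. In all these models the tabulated grade odds ratio is not estimable.

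The effect on other factors depends on the test. Under LR or score selection they lose all information in the two completely separated models, and in ATTR vs other they are estimated from grade 2-3 patients only. Under Wald selection the perfect predictor is discarded for a numerical reason. The p-values above illustrate this under assumed inputs and are not predictions for the study.

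A reader might also conclude that the study's main result is at risk, or that grade should be barred from every model. Neither follows. The primary prevalence estimate does not use these models, and grade 2 vs 3 is estimable within FAS3 and for ATTRwt vs ATTRv.

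**What to change.** Amend SAP 6.4, 8.1 and 8.2 (items 5 and 6) to state that:

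1. Grade is not a candidate in the models for positive scintigraphy, for grade 2-3 vs negative, or for ATTR vs other when grade 0 or 1 patients are included.
2. IFE and FLC results, which help define ATTR, are not candidates in any ATTR vs other model.
3. Grade 2 vs 3 may remain a candidate within FAS3 and for ATTRwt vs ATTRv.
4. The creatinine, BNP and NT-proBNP covariates in 6.4 apply only within FAS2/FAS3, in line with the exclusion already in items 5 and 6.

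It would also help to name the test used for selection and a fallback, such as Firth's penalised likelihood, should another factor separate by chance. The cost is SAP wording only: no new data and no change to study conduct or to the primary analysis.

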## **9.7. Data analysis**

Detailed methodology for summary and statistical analyses of data collected in this study will be documented in a Statistical Analysis Plan (SAP), which will be dated, filed and maintained by the sponsor. The SAP may modify the plans outlined in the protocol; any major modifications of primary endpoint definitions or their analyses would be reflected in a protocol amendment.

- Descriptive analysis will be performed for all the variables;
- Analysis will be stratified by age [50 to  $\leq 55$  ; 55 to  $\leq 60$ ; 60 to  $\leq 65$ ; 65 to  $\leq 70$ ; 70 to  $\leq 75$ ; 75 to  $\leq 80$ ; >80 years old], gender and cardiac symptomatology at entry;
- Patients with a final diagnosis of ATTR-CM will be compared with the patients who do not have a final diagnosis of ATTR-CM in order to highlight possible diagnostic red flags;
- Factors associated to ATTR amyloidosis will be identified by univariate and multivariate logistic regression. A significance level of 10% and 5% will be used for the univariate and multivariate analyses, respectively.

An interim analysis of the data collected will be performed for all the variables as soon as 75 patients will be selected with a scintigraphy grade 1, 2 or 3 and with completed e-CRF.

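### Multivariate odds ratios get ordinary 95% CIs after data-driven selection: as a set they cover well below 95%, mainly because null factors survive, and weak effects are overstated

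*SAP*

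**What the plan says.** SAP 8.1 sets a two-stage rule for logistic regression. Stage one: "If the variable is significantly associated to the outcome at the 10% level then the factor will be put forward into a multivariate model". Stage two: "backwards selection will be used to remove factors from the multivariate model which do not have a significant p value at the 5% level". The elimination goes one factor at a time: "The covariate with the highest p value will be removed in turn until all factors have a p value less than 0.05". Protocol 9.7 fixes the same levels: "A significance level of 10% and 5% will be used for the univariate and multivariate analyses, respectively".

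The candidate list is wide. SAP 8.2, Other analyses, item 5 (positive scintigraphy) "will include all variables collected in the CRF for both positive and negative scintigraphy", leaving out laboratory values. Item 6 applies the same list to grade 2-3 scans and repeats the analysis for ATTR-CM. SAP 8.1 also names the contrasts "ATTR vs other and ATTRwt vs ATTRv within patients diagnosed with ATTR-CM".

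For output, SAP 8.1 asks for "a table showing all of the 95% confidence intervals and p values for the odds ratios coming from the univariate and multivariate models". The shell of Table 15.2.2 has columns for odds ratio with 95% CI and p value, and none for selection stability. Neither document mentions a bootstrap, shrinkage, internal validation, a selection-adjusted interval, or a caveat on these CIs. SAP 4.1 and 4.2 say that no inferential hypothesis supports a claim and that all tests are exploratory.

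**The concern.** A Wald interval has its nominal coverage when the model is fixed before the data are seen. Here the same data choose the model. A single-term factor stays only if its Wald p value is below 0.05, which is the same as its 95% CI excluding 1. If its true odds ratio is 1, the printed interval is wrong every time it is printed. A weak real factor tends to survive in the samples that overestimate it, so its printed odds ratio is too large on average.

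What is at stake is the reading of the multivariate columns. The SAP says that associated factors will be identified this way, and the protocol plans publication. From an odds ratio, CI and p value alone, a reader cannot tell a chance survivor from a real factor.

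**Working it through.** **Inputs from the documents.** Entry at p<0.10 and retention at p<0.05 (SAP 8.1). N=1500 with 10% ATTR-CM (Protocol 9.5), so 150 cases. A minimum of 1000 screened (Protocol 5, amendments 2.2 and 2.3), so 100 cases at 10%. Candidates: about 38, from counting the patient-information and clinical-evaluation rows in Protocol 9.3 without the visit date, one term each.

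**The plan's own figures.** Nothing is stated about coverage. The sample-size figures do reproduce, which confirms the 150 cases: 1.96×√(0.10×0.90/1500) = 1.52% (stated 1.5%) and 1.96×√(0.30×0.70/150) = 7.33% (stated 7.3%).

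**Assumptions not in the documents.** Standardised normal candidates; 30 null factors and 8 real ones (two each with OR 1.2, 1.35, 1.5 and 2.0 per SD); correlation 0 to 0.5; Wald intervals; 400 runs per scenario. Interactions and missing data were not simulated.

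**Main setting (N=1500, 10% cases, correlation 0).** Kept per run = number offered × retention rate.

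| True OR | Offered × retention | Kept per run | Coverage if kept | Kept and covered |
|---|---|---|---|---|
| 1.0 | 30 × 0.044 | 1.320 | 0 | 0 |
| 1.2 | 2 × 0.427 | 0.854 | 0.947 | 0.809 |
| 1.35 | 2 × 0.889 | 1.778 | 0.965 | 1.716 |
| 1.5 | 2 × 0.988 | 1.976 | 0.954 | 1.885 |
| 2.0 | 2 × 1.000 | 2.000 | 0.945 | 1.890 |
| Sum | | 7.928 | | 6.300 |

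- Pooled coverage = 6.300/7.928 = 79% (80% at correlation 0.5).
- Coverage among the real factors only = 6.300/(7.928 − 1.320) = 6.300/6.608 = 95%.
- The gap is therefore the 1.3 null factors kept per run. Their apparent odds ratios average about 1.25-1.29 away from 1.
- One model with all 38 factors and no selection gave 94-95%, so selection causes the shortfall.

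**Overstatement of real effects (ratio of mean estimated to true log-OR, if kept).**

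| True OR | N=1500 | N=1000 |
|---|---|---|
| 1.2 | 1.45-1.50 | 1.76 |
| 1.35 | 1.08-1.10 | 1.21 |
| 1.5 | 1.02-1.03 | 1.06 |
| 2.0 | 1.01-1.02 | 1.01 |

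A true OR of 1.2 is thus printed as about exp(1.45×ln 1.2) = 1.30 at N=1500 and exp(1.76×ln 1.2) = 1.38 at N=1000. In the latter case its coverage is 89%.

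**Other mixes.**
- N=1000, correlation 0.3: pooled coverage 81%.
- Eight real factors, all with OR 2.0, N=1500: 85%.
- N=1000 with 40 candidates (34 null, four with OR 1.25, two with OR 1.6): 70% at 15% positive and 67% at 10% positive. About 1.5 to 1.7 null factors are kept, and weak log-ORs are inflated by 24-40%.
- All factors null: 0%.

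**ATTRwt versus ATTRv (assumed n=150, 20% ATTRv, so 30 cases).** Pooled coverage is 61%. Inflation and coverage by true OR: 1.2, 3.4 times and 71%; 1.35, 2.4 times and 80%; 1.5, 1.8 times and 92%; 2.0, 1.2 times and 95%. Here the real but weak factors undercover too. A full model without selection is no substitute: coverage is about 90% and the estimates are unstable.

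**Check of the remedy (N=1500, 38 candidates).** Bootstrapping the whole selection raised pooled coverage for retained factors from 78% to 95%. Mean inclusion frequency was about 60% for surviving null factors and 97% for strong ones. The gain comes from null survivors whose intervals now include 1. It does not promise exactly 95% for each factor, and it was not tested in the 30-case model.

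**The case against.** The strongest reply has four parts.

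1. *The tests are declared exploratory, and univariate results stand beside the multivariate ones.* True, and it limits the severity. But the label deals with claims and multiplicity. It does not change what an interval headed 95% covers, and the univariate columns do not show how stable the selection is.

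2. *Pooled coverage is a false-positive rate in another form, and it depends on the share of null candidates.* Largely right. A reader might infer that each retained factor's CI covers far less than 95%. The main-model figures do not support that: real factors keep about 95%, apart from 89% for OR 1.2 at N=1000. The defect belongs to the reported set, and the printed table gives no means of separating the two kinds of factor.

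3. *Not every retained interval excludes 1.* Correct. SAP 8.1 keeps the component factors of a significant interaction whatever their p values. A multi-level factor such as age class or NYHA class can be significant overall while single levels are not. In a simulated four-level factor (n=1000, assumed ORs 1.3, 1.6 and 2.0), 87% of retained cases had at least one level whose CI included 1. When that factor was null, 69% of the level CIs still covered 1. The 0% statement is confined to single-term factors kept on their own p value.

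4. *The red flags come from elsewhere.* A reader might take Table 15.2.2 as the source of the diagnostic red flags. Protocol 9.7 and SAP 8.2, Other analyses, item 4 list that comparison separately from the regressions, and Table 15.2.2 models positive scintigraphy, not ATTR-CM. This point therefore concerns the regression tables only.

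**Conclusion.** The concern holds in a limited form. The plan prints unadjusted 95% CIs and p values after data-driven selection from a long candidate list. The reported set then covers well below 95%, driven by null survivors, and weak odds ratios are overstated. Effects of OR 1.5 per SD and above are nearly unaffected in the main models, as is OR 1.35 at N=1500. The problem is worse for ATTRwt versus ATTRv.

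The ranges (about 67-85% pooled in mixes with some real effects; about 61% for ATTRwt versus ATTRv) depend on assumed numbers of null factors, effect sizes and ATTRv share. No single coverage figure can be attributed to the plan. The direction needs no simulation, because it follows from the retention rule. This is a secondary, exploratory analysis, and the primary prevalence with its Wilson CI is not affected. The change is worth making before the regression tables are released.

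**What to change.** Keep the SAP 8.1 model and add the following for each multivariate model:

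- Bootstrap patients and repeat the entire procedure (10% screen, then elimination to p<0.05) in each resample, for example 500 times.
- Add two columns to Table 15.2.2 and its ATTR-CM and ATTRwt/ATTRv counterparts: the factor's inclusion frequency, and a resampling-based interval with the log-OR entered as 0 in resamples where the factor drops out.
- Footnote any Wald CI that remains as not adjusted for selection.
- For ATTRwt versus ATTRv, also report how many resamples failed to fit, since few ATTRv cases are likely.

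The cost is a little programming and no new data. The downside is wider intervals, and somewhat smaller weak odds ratios if the resampled estimate is reported. If only one change is made, the footnote is the minimum, but it would not show which factors are unstable.

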### **3 INTERIM ANALYSES**

*An interim analysis of the data collected was planned for all the variables as soon as 75 patients will be selected with a scintigraphy grade 1, 2 or 3 and with completed e-CRF. This interim analysis was finally not performed.*

In addition, an interim analysis was performed for publication purpose, all patients screened until the May 11th 2020 were included in this analysis. Considering the expected number of patients with a scintigraphy grade 1, 2 or 3, all analyses described in this SAP were done, except multivariate analyses planned in 0.

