## 4.2 STATISTICAL DECISION RULES

The analysis of this study will be mainly descriptive. However, factors associated to ATTR will be identified using a multivariate analysis. All statistical tests will be exploratory in nature.

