### 6. Factors associated to grade 2-3 scintigraphy and ATTR-CM

Factors associated to grade 2 or 3 will be identified in the FAS1 by univariate and multivariate logistic regression (compared with negative patients). This analysis will be performed in the FAS1 population and will include all variables collected in the CRF for both positive and negative scintigraphy. Clinical laboratories will be excluded from this analysis as only available for positive scintigraphy. The same analysis will be repeated to identify factors associated to ATTR-CM (FAS 2 & 3).

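### SAP 8.1 tests every pairwise interaction with no stated level, short list or multiplicity control, and names the same procedure for ATTRwt vs ATTRv with no cap tied to the number of events

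*SAP*

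**What the plan says.** SAP 8.1 fits one logistic model per factor. A factor moves to the multivariate model under the condition "If the variable is significantly associated to the outcome at the 10% level". Backward selection then removes factors "which do not have a significant p value at the 5% level". On interactions, the section says "A significant interaction is tested for between all variables in the multivariate model", and adds: "If a significant interaction is found then the individual factors of this interaction will be kept in the model, regardless of their p value". It gives no significance level for the interaction tests and does not say whether they come before or after backward selection. It sets no list of interactions, multiplicity control, limit on parameters or method for sparse data.

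The outcomes named in 8.1 are "ATTR vs other and ATTRwt vs ATTRv within patients diagnosed with ATTR-CM". SAP 8.2 does not match this. Under Other analyses, items 5 and 6 plan regressions for positive scintigraphy, grade 2-3 scintigraphy and ATTR-CM. For ATTRv and ATTRwt, item 3 plans description only. Protocol 9.7 mentions regression only for ATTR amyloidosis.

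For the models in FAS1, the candidate set "will include all variables collected in the CRF for both positive and negative scintigraphy", with laboratory results left out. SAP section 7 does not impute missing data. SAP 4.2 states: "All statistical tests will be exploratory in nature".

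**The concern.** The number of pairwise tests grows with the square of the number of factors, so an open-ended search can produce interactions by chance even when none exists. Any interaction found this way also holds its two main effects in the model, and the resulting odds ratios and p values are tabulated.

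For ATTRwt vs ATTRv the effective sample size is the smaller genotype group. A procedure with no parameter limit can ask more of that group than it can give, and some interaction terms may have no finite estimate.

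The sponsor has already met a version of this problem. SAP section 3 reports that, at the interim analysis for publication and in view of the expected number of grade 1-3 patients, "all analyses described in this SAP were done, except multivariate analyses planned in 0". The final analysis has no corresponding threshold. At stake is how far the exploratory list of associated factors can be trusted, not the primary result.

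**Working it through.** **The plan's own figures.** Neither document gives an error rate for interactions or a number of ATTRv patients. The stated precision in protocol 9.5 does reproduce, and it fixes the number of ATTR-CM patients assumed:
- 1.96 × √(0.10 × 0.90 / 1500) = 1.52%, stated as ±1.5%.
- 10% of 1500 = 150 ATTR-CM patients; 1.96 × √(0.30 × 0.70 / 150) = 7.33%, stated as ±7.3%.

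The protocol's abstract milestones also allow data collection to end at 1000 screened, which gives 10% × 1000 = 100 ATTR-CM patients. The working range is therefore 100-150.

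**False-positive interactions.** With k factors there are m = k(k−1)/2 pairs. At an assumed 5% level, with independent tests and no true interaction, the chance of at least one false positive is 1 − 0.95^m, and the expected number is 0.05m.

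| k | m | Expected false positives | Chance of at least one |
|---|---|---|---|
| 3 | 3 | 0.15 | 14% |
| 5 | 10 | 0.50 | 40% |
| 8 | 28 | 1.40 | 76% |
| 10 | 45 | 2.25 | 90% |

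A simulation without the independence formula agrees. It used 1500 patients, about 150 events and independent binary factors (prevalence 0.4, log odds ratio 0.5) with no true interaction, and tested each pair by likelihood ratio at 5% over 200 runs. At least one false positive occurred in 44.5% of runs at k = 5, 70.5% at k = 8 and 93.0% at k = 10.

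**How many factors?** The plan does not say. Protocol 9.3 lists 33 clinical-evaluation rows (excluding the date) and 5 patient-information rows; three family-history items bring this to about 40. If all were unrelated to the outcome, 40 × 0.10 = 4 would pass the screen, giving 6 pairs and 1 − 0.95^6 = 26%. If interactions are tested only after backward selection, about half of those would remain (0.05/0.10), leaving one pair and 5%. Genuine predictors add to either count by an unknown number.

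**ATTRwt vs ATTRv.** The ATTRv share is an assumption, shown as a range. All ATTR patients are taken as genotyped, ATTRv is the smaller group, and ten events per parameter is used as a rule of thumb.

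| Assumed ATTRv share | Events of 100 | Parameters | Events of 150 | Parameters |
|---|---|---|---|---|
| 5% | 5 | 0.5 | 7.5 | 0.75 |
| 10% | 10 | 1.0 | 15 | 1.5 |
| 20% | 20 | 2.0 | 30 | 3.0 |
| 30% | 30 | 3.0 | 45 | 4.5 |

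Five single-parameter factors plus their ten interactions need 15 parameters, so there would be 5/15 = 0.3 to 45/15 = 3 events per parameter. Protocol 9.2.4 collects genotype only where it was done in routine care, so the true counts may be lower.

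The same kind of simulation with 150 patients (300 runs) shows when fitting breaks down:
- About 7.5 events, 3-5 factors: the main-effects model failed in 8-15% of runs, and 41-46% of single interaction terms could not be estimated.
- 15 events, 3-8 factors: 0-1% and 8-9%.
- 30 events, 3-8 factors: 0% and at most 0.2%.

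**The case against.** SAP 4.1 and 4.2 disclaim any inferential claim and label every test exploratory. Univariate and multivariate results are both tabulated, so a reader can see part of the selection. That limits the consequence, but it does not lower the false-positive rate or say which interactions were of interest.

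Several stronger readings are tempting and not supported:
- A reader might infer that interactions are tested at 5%. That level is stated for backward removal only; its use for interactions is an assumption.
- A reader might infer that spurious interactions are near certain. That needs about ten or more factors. With 3-5 the chance is 14-40%, and it could be lower if testing follows backward selection.
- A reader might infer that the ATTRv model cannot be fitted. The documents give no ATTRv count. Frequent failure appears only near 7 events, and with 30 or more a small main-effects model fits.
- A reader might fault the rule that retains main effects under an interaction. That is the ordinary hierarchy principle.
- A reader might carry the sparse-data problem over to the diagnostic red flags. Those come from comparing ATTR-CM with patients without it, where the plan expects 100-150 events.

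The objection that the ATTRwt vs ATTRv model may not be planned at all has force, given 8.2. It turns that part of the point into a mismatch to be resolved. The interim omission is also weaker evidence than it looks, since it concerned the number of grade 1-3 patients rather than the genotype groups.

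**Conclusion.** The point holds as a minor one. SAP 8.1 prescribes an unrestricted interaction search with no stated level or multiplicity control. At an assumed 5% level the chance of at least one false positive is about 14%, 40% and 90% with 3, 5 and 10 factors; where the study falls on that scale is unknown.

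For ATTRwt vs ATTRv, sections 8.1 and 8.2 disagree on whether a model is planned. If it is, an assumed 5-30% ATTRv share of 100-150 genotyped patients gives about 5-45 events and supports roughly 0.5-4.5 parameters, with no cap or sparse-data method written in. At the low end many interaction terms could not be estimated; at 30 or more events the case is against the interaction search, not against a small main-effects model. The primary prevalence estimate is unaffected.

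**What to change.** In SAP 8.1, delete the all-pairs interaction test. Alternatively, name a few interactions before the analysis, state their level with a multiplicity adjustment, and say at what step they are tested. As an illustration, a Bonferroni level for three named interactions would be 0.05/3 = 0.017, against 0.05/45 = 0.0011 for all pairs of ten factors.

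For ATTRwt vs ATTRv, report univariate odds ratios only, or a Firth penalised logistic model limited to about one parameter per ten events in the smaller genotype group, without interactions. Then make 8.1 and 8.2 agree on whether that comparison is modelled or only described.

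The cost is SAP wording and fewer exploratory outputs. The real downside is that an unanticipated interaction could be missed.
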